9.3. Populations for Analyses

For purposes of analysis, the following populations are defined:

| Population | Description |
|-------------------|---|
| Full analysis set | The FAS is defined as all randomized subjects in the study, with at least one measurement of the primary efficacy variable following at least one dose of study medication. Summaries on the FAS will be performed for all efficacy endpoints. Subjects in this |

| | |
|--------------|---|
| | analysis set will be summarized according to the treatment they were randomly assigned to. |
| Per Protocol | The PP Set will be a subset of subjects in the FAS who completed the study and for whom no relevant protocol deviations were documented. Identification of relevant protocol deviations will occur on a blinded review meeting preceding database lock. A second analysis of the primary efficacy endpoint will be based on the PP Set. All subjects in the PP Set will be summarized according to the treatment they were assigned to. |
| Safety | The Safety Set will include all randomized subjects assigned to study intervention and who take at least 1 dose of study medication. The Safety Set will be used for the analysis of all safety endpoints. All subjects in the Safety Set will be summarized according to the treatment they actually received (according to the Drug Accountability eCRF page). |

The decision whether a protocol deviation is relevant or not for the exclusion of participants from the per protocol (PP) set will be made case-by-case in a blind data review meeting.

The primary analysis of the primary efficacy variable will be based on the FAS data set. A secondary analysis of the primary efficacy parameter will be based on the PP set.

All other secondary efficacy analyses will be based on the FAS.

Safety analyses will be based on the safety analysis (SA) set.

9.4. Statistical Analyses

The statistical analysis plan will be developed and finalized before database lock and will describe the participant populations to be included in the analyses, and procedures for accounting for missing, unused, and spurious data. This section is a summary of the planned statistical analyses of the primary and secondary endpoints.

9.4.1. Efficacy Analyses

- Primary efficacy endpoint

The primary endpoint evaluated in this study is the mean change in pain severity (“average worst pain experienced in the last 7 days”, i.e. average of the worst pain score on each of the 7 days preceding the site visit), as assessed by an 11-point NRS, from baseline to Week 16.

The primary efficacy endpoint, change from baseline to Week 16 in pain severity score, will be analyzed using a mixed model repeated measures (MMRM) using visit on subject ID as the repeated factor with unstructured covariance term.

The model will include fixed effects terms for treatment, country, visit and regular pain medication use at baseline (yes or no) and covariate term for pain severity score at baseline.

- Secondary efficacy endpoint

Percentage of pain responders defined as subjects with reduction in pain severity of ≥ 2 points (“average worst pain experienced in the last 7 days”), at weeks 4, 8 and 16 as assessed by an 11-point NRS, compared to baseline;

The pain severity score (average worst pain score using 11 point NRS scale) at weeks 4 and 8;

The Clinical Global Impression of Severity (CGI-S) score at weeks 4, 8 and 16 (rated by Investigator);

The change from baseline to Weeks 4, 8 and 16 in the Clinical Global Impression of Change (CGI-C) score rated by Investigator;

The change from baseline to Weeks 4, 8 and 16 in the Patient Global Impression of Change (PGI-C) score rated by the subject;

The percentage of subjects with a reduction in the number of days using concomitant pain drugs in the 7 days before each visit at Weeks 4, 8 and 16;

The number of days with PRN pain medication in the 7 days before each visit at weeks 4, 8 and 16;

The change from baseline to week 16 in the Hospital Anxiety and Depression Scale (HADS) score;

The change from baseline to weeks 4, 8 and 16 in the Movement Disorder Society - Unified Parkinson’s Disease Rating Scale (MDS-UPDRS) (total score and subscores) during the “ON” phase;

Percentage of pain responders defined as subjects with reduction in pain severity of ≥ 2 points (“average worst pain experienced in the last 7 days”) as assessed by an 11-point NRS, compared to baseline), will be analysed at weeks 4, 8 and 16 using a Cochran-

Mantel-Haenszel adjusted test of the difference in proportions between the two treatment groups. Country will be used as the stratification factor.

The analysis of amount of concomitant PRN PD pain medication (as reported in the Patient Diary) and concomitant pain drugs (as reported on the “Concomitant Medication” eCRF page) will be done in the same way at weeks 4, 8 and 16

PGI-C, CGI-C, CGI-S, and MDS-UPDRS will be analysed at weeks 4, 8 and 16 using the same statistical method as for the primary efficacy parameter.

Change from baseline in HADS at Week 16 will be analysed using an ANCOVA. The model will include treatment, baseline HADS and country as fixed effects.

9.4.2. Safety Analyses

All safety analyses will be performed on the Safety Population.

Descriptive statistics analysis will be applied to safety variables and the summaries will be presented in descending order of frequency by SOC. Likewise, within each SOC, the PTs will be presented by descending order of frequency.

9.4.3. Baseline Descriptive Analyses

Data collected at screening visit (i.e. age, sex, ethnicity, smoking and alcohol use, MMSE score, Hoehn and Yahr stage, duration of PD, as well as the participant’s Medical History, Prior and Concomitant medication) will be tabulated with descriptive statistics or counts/percentages depending on the variable and where appropriate.

9.5. Interim Analyses

No interim analysis planned.

9.5.1. Data Monitoring Committee (DMC)

No Data Monitoring Committee planned.

10. Supporting Documentation and Operational Considerations

10.1. Appendix 1: Regulatory, Ethical, and Study Oversight Considerations

10.1.1. Regulatory and Ethical Considerations

- This study will be conducted in accordance with the protocol and with the following:
 - Consensus ethical principles derived from international guidelines including the Declaration of Helsinki and Council for International Organizations of Medical Sciences (CIOMS) International Ethical Guidelines
 - Applicable ICH Good Clinical Practice (GCP) Guidelines
 - Applicable laws and regulations
- The protocol, protocol amendments, ICF, Investigator Brochure, and other relevant documents (eg, advertisements) must be submitted to an IRB/IEC by the investigator and reviewed and approved by the IRB/IEC before the study is initiated.
- Any amendments to the protocol will require IRB/IEC approval before implementation of changes made to the study design, except for changes necessary to eliminate an immediate hazard to study participants.
- The investigator will be responsible for the following:
 - Providing written summaries of the status of the study to the IRB/IEC annually or more frequently in accordance with the requirements, policies, and procedures established by the IRB/IEC
 - Notifying the IRB/IEC of SAEs or other significant safety findings as required by IRB/IEC procedures
 - Providing oversight of the conduct of the study at the site and adherence to requirements of 21 CFR, ICH guidelines, the IRB/IEC, European regulation 536/2014 for clinical studies (if applicable), and all other applicable local regulations

10.1.2. Financial Disclosure

Investigators and sub-investigators will provide the sponsor with sufficient, accurate financial information as requested to allow the sponsor to submit complete and accurate financial certification or disclosure statements to the appropriate regulatory authorities. Investigators are responsible for providing information on financial interests during the course of the study and for 1 year after completion of the study.

10.1.3. Informed Consent Process

- The investigator or his/her representative will explain the nature of the study to the participant or his/her legally authorized representative and answer all questions regarding the study.
- Participants must be informed that their participation is voluntary. Participants or their legally authorized representative will be required to sign a statement of informed consent

that meets the requirements of ICH E6 (R2) Good clinical practice, local regulations, Regulation (EU) 2016/679 (GDPR) requirements, where applicable, and the IRB/IEC or study center.

- The medical record must include a statement that written informed consent was obtained before the participant was enrolled in the study and the date the written consent was obtained. The authorized person obtaining the informed consent must also sign the ICF.
- Participants must be re-consented to the most current version of the ICF(s) during their participation in the study.
- A copy of the ICF(s) must be provided to the participant or the participant's legally authorized representative.

10.1.4. Data Protection

- Participants will be assigned a unique identifier by the sponsor. Any participant records or datasets that are transferred to the sponsor will contain the identifier only; participant names or any information which would make the participant identifiable will not be transferred.
- The participant must be informed that his/her personal study-related data will be used by the sponsor in accordance with local data protection law. The level of disclosure must also be explained to the participant.
- The participant must be informed that his/her medical records may be examined by Clinical Quality Assurance auditors or other authorized personnel appointed by the sponsor, by appropriate IRB/IEC members, and by inspectors from regulatory authorities.

10.1.5. Committees Structure

Internal approval process involves protocol reviewed by the Protocol Review Committee, Pharmacovigilance & Quality Assurance.

10.1.6. Dissemination of Clinical Study Data

A Clinical Trial Report of the study will be prepared and written by the CRO according to ICH topic E3 (CPMP/ICH/137/95). A summary of the report will be sent to Investigators / ECs / Regulatory Authorities, according to current regulations.

10.1.7. Data Quality Assurance

- All participant data relating to the study will be recorded on electronic CRF unless transmitted to the sponsor or designee electronically (eg, laboratory data). The investigator is responsible for verifying that data entries are accurate and correct by physically or electronically signing the CRF.
- The investigator must maintain accurate documentation (source data) that supports the information entered in the CRF.
- The investigator must permit study-related monitoring, audits, IRB/IEC review, and regulatory agency inspections and provide direct access to source data documents.

- The sponsor or designee is responsible for the data management of this study including quality checking of the data.
- Study monitors will perform ongoing source data verification to confirm that data entered into the CRF by authorized site personnel are accurate, complete, and verifiable from source documents; that the safety and rights of participants are being protected; and that the study is being conducted in accordance with the currently approved protocol and any other study agreements, ICH GCP, and all applicable regulatory requirements.
- Records and documents, including signed ICFs, pertaining to the conduct of this study must be retained by the investigator for 15 years after study completion unless local regulations or institutional policies require a longer retention period. No records may be destroyed during the retention period without the written approval of the sponsor. No records may be transferred to another location or party without written notification to the sponsor.

10.1.8. Source Documents

- Source documents provide evidence for the existence of the participant and substantiate the integrity of the data collected. Source documents are filed at the investigator's site.
- Data reported on the CRF or entered in the eCRF that are transcribed from source documents must be consistent with the source documents or the discrepancies must be explained. The investigator may need to request previous medical records or transfer records, depending on the study. Also, current medical records must be available.
- As per ICH E6 document, section 1.52, source documents are defined as "Original documents, data and records (e.g., hospital records, clinical and office charts, laboratory notes, memoranda, participants' diaries of evaluation checklists, pharmacy dispensing records, recorded data from automated instruments, copies or transcriptions certified after verification as being accurate and complete, microfiches, photographic negatives, microfilm or magnetic media, x-rays, subject files, and records kept at the pharmacy, at the laboratories, and at medico-technical departments involved in the clinical trial).

10.1.9. Study and Site Closure

The sponsor designee reserves the right to close the study site or terminate the study at any time for any reason at the sole discretion of the sponsor. Study sites will be closed upon study completion. A study site is considered closed when all required documents and study supplies have been collected and a study-site closure visit has been performed.

The investigator may initiate study-site closure at any time, provided there is reasonable cause and sufficient notice is given in advance of the intended termination.

Reasons for the early closure of a study site by the sponsor or investigator may include but are not limited to:

- Failure of the investigator to comply with the protocol, the requirements of the IRB/IEC or local health authorities, the sponsor's procedures, or GCP guidelines
- Inadequate recruitment of participants by the investigator
- Discontinuation of further study intervention development

10.1.10. Publication Policy

- The results of this study may be published or presented at scientific meetings. If this is foreseen, the investigator agrees to submit all manuscripts or abstracts to the sponsor before submission. This allows the sponsor to protect proprietary information and to provide comments.
- The sponsor will comply with the requirements for publication of study results. In accordance with standard editorial and ethical practice, the sponsor will generally support publication of multicenter studies only in their entirety and not as individual site data. In this case, a coordinating investigator will be designated by mutual agreement.
- Authorship will be determined by mutual agreement and in line with International Committee of Medical Journal Editors authorship requirements.

10.2. Appendix 2: Clinical Laboratory Tests

- The tests detailed in Table 1 will be performed by the local laboratory.
- If the local laboratory results are used to make either a study intervention decision or response evaluation, the results must be entered into the eCRF.
- Protocol-specific requirements for inclusion or exclusion of participants are detailed in Section 5 of the protocol.
- Additional tests may be performed at any time during the study as determined necessary by the investigator or required by local regulations.
- Investigators must document their review of each laboratory safety report, by signing and dating it.

Table 1 Protocol-Required Safety Laboratory Assessments

| Laboratory Assessments | Parameters | | | |
|------------------------|---------------------------------|-----------|--|------------------------------|
| Hematology | Platelet Count | | White blood cell (WBC) count with Differential: Neutrophils Lymphocytes Monocytes Eosinophils Basophils | |
| | Red blood cell (RBC) Count | | | |
| | Hemoglobin | | | |
| | Hematocrit | | | |
| Clinical Chemistry | Blood urea nitrogen (BUN) | Potassium | Aspartate Aminotransferase (AST)/ Serum Glutamic-Oxaloacetic Transaminase (SGOT) | Total and direct bilirubin |
| | Creatinine | Sodium | Alanine Aminotransferase (ALT)/ Serum Glutamic-Pyruvic Transaminase (SGPT) | Total Protein |
| | | Calcium | Alkaline phosphatase | Gamma-glutamyltranspeptidase |
| Pregnancy Tests: | Dipstick - urine pregnancy test | | | |

NOTES :

¹ All events of ALT $\geq 3 \times$ upper limit of normal (ULN) and bilirubin $\geq 2 \times$ ULN ($>35\%$ direct bilirubin) or ALT $\geq 3 \times$ ULN and international normalized ratio (INR) >1.5 , if INR measured which may indicate severe liver injury (possible Hy's Law), must be reported as an SAE (excluding studies of hepatic impairment or cirrhosis).

10.3. Appendix 3: Adverse Events: Definitions and Procedures for Recording, Evaluating, Follow-up, and Reporting

Definition of AE

AE Definition

- An AE is any untoward medical occurrence in a patient or clinical study participant, temporally associated with the use of study intervention, whether or not considered related to the study intervention.
- NOTE: An AE can therefore be any unfavorable and unintended sign (including an abnormal laboratory finding), symptom, or disease (new or exacerbated) temporally associated with the use of study intervention.

Events Meeting the AE Definition

- Any abnormal laboratory test results (hematology, clinical chemistry, or urinalysis) or other safety assessments (eg, ECG, radiological scans, vital signs measurements), including those that worsen from baseline, considered clinically significant in the medical and scientific judgment of the investigator (ie, not related to progression of underlying disease).
- Exacerbation of a chronic or intermittent pre-existing condition including either an increase in frequency and/or intensity of the condition.
- New conditions detected or diagnosed after study intervention administration even though it may have been present before the start of the study.
- Signs, symptoms, or the clinical sequelae of a suspected drug-drug interaction.
- Signs, symptoms, or the clinical sequelae of a suspected overdose of either study intervention or a concomitant medication. Overdose per se will not be reported as an AE/SAE unless it is an intentional overdose taken with possible suicidal/self-harming intent. Such overdoses should be reported regardless of sequelae.
- "Lack of efficacy" or "failure of expected pharmacological action" per se will not be reported as an AE or SAE. Such instances will be captured in the efficacy assessments. However, the signs, symptoms, and/or clinical sequelae resulting from lack of efficacy will be reported as AE or SAE if they fulfil the definition of an AE or SAE.
- The signs, symptoms, and/or clinical sequelae resulting from lack of efficacy will be reported as AE or SAE if they fulfil the definition of an AE or SAE. Also, "lack of efficacy" or "failure of expected pharmacological action" also constitutes an AE or SAE.

Events NOT Meeting the AE Definition

- Any clinically significant abnormal laboratory findings or other abnormal safety assessments which are associated with the underlying disease, unless judged by the investigator to be more severe than expected for the participant's condition.
- The disease/disorder being studied or expected progression, signs, or symptoms of the disease/disorder being studied, unless more severe than expected for the participant's condition.
- Medical or surgical procedure (eg, endoscopy, appendectomy): the condition that leads to the procedure is the AE.
- Situations in which an untoward medical occurrence did not occur (social and/or convenience admission to a hospital).
- Anticipated day-to-day fluctuations of pre-existing disease(s) or condition(s) present or detected at the start of the study that do not worsen.

Definition of SAE

If an event is not an AE per definition above, then it cannot be an SAE even if serious conditions are met (eg, hospitalization for signs/symptoms of the disease under study, death due to progression of disease).

A SAE is defined as any untoward medical occurrence that, at any dose:

a. Results in death

b. Is life-threatening

The term 'life-threatening' in the definition of 'serious' refers to an event in which the participant was at risk of death at the time of the event. It does not refer to an event, which hypothetically might have caused death, if it were more severe.

c. Requires inpatient hospitalization or prolongation of existing hospitalization

In general, hospitalization signifies that the participant has been detained (usually involving at least an overnight stay) at the hospital or emergency ward for observation and/or treatment that would not have been appropriate in the physician's office or outpatient setting. Complications that occur during hospitalization are AEs. If a complication prolongs hospitalization or fulfills any other serious criteria, the event is serious. When in doubt as to whether "hospitalization" occurred or was necessary, the AE should be considered serious.

Hospitalization for elective treatment of a pre-existing condition that did not worsen from baseline is not considered an AE.

d. Results in persistent disability/incapacity

- The term disability means a substantial disruption of a person's ability to conduct normal life functions.
- This definition is not intended to include experiences of relatively minor medical significance such as uncomplicated headache, nausea, vomiting, diarrhea, influenza, and accidental trauma (eg, sprained ankle) which may interfere with or prevent everyday life functions but do not constitute a substantial disruption.

e. Is a congenital anomaly/birth defect

f. Other situations:

- Medical or scientific judgment should be exercised in deciding whether SAE reporting is appropriate in other situations such as important medical events that may not be immediately life-threatening or result in death or hospitalization but may jeopardize the participant or may require medical or surgical intervention to prevent one of the other outcomes listed in the above definition. These events should usually be considered serious.

Examples of such events include invasive or malignant cancers, intensive treatment in an emergency room or at home for allergic bronchospasm, blood dyscrasias or convulsions that do not result in hospitalization, or development of drug dependency or drug abuse.

Recording and Follow-Up of AE and/or SAE

AE and SAE Recording

- When an AE/SAE occurs, it is the responsibility of the investigator to review all documentation (eg, hospital progress notes, laboratory reports, and diagnostics reports) related to the event.
- The investigator will then record all relevant AE/SAE information in the CRF.
- It is **not** acceptable for the investigator to send photocopies of the participant's medical records to CRO's Pharmacovigilance in lieu of completion of the AE/SAE CRF page.
- There may be instances when copies of medical records for certain cases are requested by the Medical Monitor or Pharmacovigilance. In this case, all participant identifiers, with the exception of the participant number, will be redacted on the copies of the medical records before submission to the requestor.
- The investigator will attempt to establish a diagnosis of the event based on signs, symptoms, and/or other clinical information. Whenever possible, the diagnosis (not the individual signs/symptoms) will be documented as the AE/SAE.

Assessment of Intensity

The investigator will make an assessment of intensity for each AE and SAE reported during the study and assign it to 1 of the following categories:

- Mild: An event that is easily tolerated by the participant, causing minimal discomfort and not interfering with everyday activities.
- Moderate: An event that causes sufficient discomfort and interferes with normal everyday activities.
- Severe: An event that prevents normal everyday activities. An AE that is assessed as severe should not be confused with a SAE. Severe is a category utilized for rating the intensity of an event; and both AEs and SAEs can be assessed as severe.

An event is defined as 'serious' when it meets at least 1 of the predefined outcomes as described in the definition of an SAE, NOT when it is rated as severe.

Assessment of Causality

- The investigator is obligated to assess the relationship between study intervention and each occurrence of each AE/SAE.
- A "reasonable possibility" of a relationship conveys that there are facts, evidence, and/or arguments to suggest a causal relationship, rather than a relationship cannot be ruled out.
- The investigator will use clinical judgment to determine the relationship.
- Alternative causes, such as underlying disease(s), concomitant therapy, and other risk factors, as well as the temporal relationship of the event to study intervention administration will be considered and investigated.
- The investigator will also consult the Summary of Product Characteristics of Safinamide in his/her assessment.
- For each AE/SAE, the investigator **must** document in the medical notes that he/she has reviewed the AE/SAE and has provided an assessment of causality.
- There may be situations in which an SAE has occurred and the investigator has minimal information to include in the initial report to Pharmacovigilance. However, **it is very important that the investigator always make an assessment of causality for every event before the initial transmission of the SAE data to Pharmacovigilance.**
- The investigator may change his/her opinion of causality in light of follow-up information and send a SAE follow-up report with the updated causality assessment.
- The causality assessment is one of the criteria used when determining regulatory reporting requirements.

Follow-up of AEs and SAEs

- The investigator is obligated to perform or arrange for the conduct of supplemental measurements and/or evaluations as medically indicated or as requested by sponsor to elucidate the nature and/or causality of the AE or SAE as fully as possible. This may include additional laboratory tests or investigations, histopathological examinations, or consultation with other health care professionals.
- If a participant dies during participation in the study or during a recognized follow-up period, the investigator will provide CRO's Pharmacovigilance with a copy of any post-mortem findings including histopathology.
- New or updated information will be recorded in the originally completed CRF.
- The investigator will submit any updated SAE data to pharmacovigilance within 24 hours of receipt of the information.

Reporting of SAEs

SAE Reporting to Pharmacovigilance via an Electronic Data Collection Tool

- The primary mechanism for reporting an SAE to Pharmacovigilance will be the electronic data collection tool.
- If the electronic system is unavailable for more than 24 hours, then the site will use the paper SAE data collection tool (see next section).
- The site will enter the SAE data into the electronic system as soon as it becomes available.
- After the study is completed at a given site, the electronic data collection tool will be taken off-line to prevent the entry of new data or changes to existing data.
- If a site receives a report of a new SAE from a study participant or receives updated data on a previously reported SAE after the electronic data collection tool has been taken off-line, then the site can report this information on a paper SAE form (see next section) or to the medical monitor by telephone.
- Contacts for SAE reporting can be found in the Investigator Study File.

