All adverse events will be classified by SOC and PT according to MedDRA (Version 21.0). Percentages will be calculated based on the number of subjects in the Safety Set, unless otherwise specified.

An overview summary of the number and percentage of subjects with any TEAE, serious TEAE, study drug-related TEAE, study drug-related serious TEAE, TEAE leading to study discontinuation/ early withdrawal, TEAE leading to treatment discontinuation, and AE leading to death will be provided by treatment group.

Summaries of the total number of TEAEs and the number and percentage of subjects with at least one TEAE will be provided by treatment group and overall. TEAEs will be presented in descending order of frequency by SOC. Likewise, within each SOC, the PTs will be presented by descending order of frequency.

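### Two adjacent protocol bullets give opposite rules on whether lack of efficacy is an adverse event, so TEAE incidence depends on which one a site follows

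*Protocol*

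**What the plan says.** Protocol Appendix 3 (Section 10.3), in the list of events meeting the AE definition, has two consecutive bullets on lack of efficacy or failure of the expected drug action.

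- The first says that it "per se will not be reported as an AE or SAE. Such instances will be captured in the efficacy assessments".
- The second ends by saying that "lack of efficacy' or 'failure of expected pharmacological action' also constitutes an AE or SAE".

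Both bullets also say that the consequences "resulting from lack of efficacy will be reported as AE or SAE if they fulfil the definition of an AE or SAE", so on consequences they do not differ.

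SAP 3.2 says that tolerability will be assessed by the incidence of treatment-emergent adverse events. SAP 11.1 plans, by treatment group, "An overview summary of the number and percentage of subjects with any TEAE, serious TEAE, study drug-related TEAE" and further categories. SAP 11.1.1 to 11.1.6 break these down by term, severity, relationship, seriousness and discontinuation.

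**The concern.** On lack of efficacy in itself, a site cannot obey both bullets. Neither carries a condition saying when it applies, so sites may reasonably differ, and AE counts would then mix two reporting rules in an international multicentre trial.

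The conflict matters more here than in many trials because lack of efficacy in a placebo-controlled pain study is closely tied to the efficacy outcome. If safinamide works, lack of efficacy should be more frequent on placebo. Recording it as an AE would then carry part of the efficacy contrast into the tolerability table. Blinding does not prevent this, because the imbalance would come from true response.

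Discontinuation tables may be affected as well. The SAP 6.1 list of reasons for leaving the study includes adverse event but not lack of efficacy. The same withdrawal could be coded as an adverse event under the second bullet and as, for example, other under the first. SAP 11.1.6 builds its table from that code.

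**Working it through.** **Is the conflict settled elsewhere?**

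| Place | Content | Settles it? |
|---|---|---|
| Appendix 3, first bullet | Not an AE or SAE; left to the efficacy assessments | Opposed by the next bullet |
| Appendix 3, second bullet | Is an AE or SAE | Opposed by the previous bullet |
| Appendix 3, events not meeting the AE definition | Excludes "The disease/disorder being studied or expected progression, signs, or symptoms of the disease/disorder being studied, unless more severe than expected" for that participant | No; does not name lack of efficacy |
| Protocol 8.3.6, disease-related events | Not applicable | No |
| SAP 11.1 | General AE definition only | No |
| SAP 12, changes to the planned analysis | Concerns only the global impression endpoints | No |

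**How far does it reach SAEs?** Appendix 3 states: "If an event is not an AE per definition above, then it cannot be an SAE even if serious conditions are met". AE status is therefore a precondition, and the choice of bullet could decide whether the 24-hour reporting in Protocol 8.3.1 applies. But Appendix 3 also states: "An event is defined as 'serious' when it meets at least 1 of the predefined outcomes as described in the definition of an SAE". Pain that merely fails to improve would seldom reach such an outcome, and consequences that do are handled alike by both bullets. The SAE effect is real but narrow.

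**How much could TEAE incidence move?** The plan states no figure to reproduce, and every rate below is an assumption.

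Inputs:
- b = 40%, background incidence of any other TEAE, equal in both arms (assumed).
- s = share of participants at sites that follow the second bullet (0, 0.5 or 1).
- L = share of participants for whom lack of efficacy would be recorded (assumed range).
- Lack-of-efficacy reports are taken as independent of other TEAEs.

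Formula: any-TEAE incidence = b + (1 − b) × s × L. The factor (1 − b) is needed because a participant who already has another TEAE is counted only once.

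Worked example with s = 1, L = 5% active and 10% placebo:
- Active: 0.40 + 0.60 × 0.05 = 43%
- Placebo: 0.40 + 0.60 × 0.10 = 46%
- Difference: −3 points

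| L active / placebo | s = 0 | s = 0.5 | s = 1 |
|---|---|---|---|
| 5% / 10% | 40 vs 40 (0) | 41.5 vs 43 (−1.5) | 43 vs 46 (−3) |
| 10% / 20% | 40 vs 40 (0) | 43 vs 46 (−3) | 46 vs 52 (−6) |
| 15% / 30% | 40 vs 40 (0) | 44.5 vs 49 (−4.5) | 49 vs 58 (−9) |
| 20% / 20% | 40 vs 40 (0) | 46 vs 46 (0) | 52 vs 52 (0) |

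Cells are % active vs % placebo, with the difference in points.

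Extreme case with s = 1, L = 50% active and 70% placebo:
- Active: 0.40 + 0.60 × 0.50 = 70%
- Placebo: 0.40 + 0.60 × 0.70 = 82%
- Difference: −12 points

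With equal L there is no between-arm shift, but both arms rise from 40% to 52% at s = 1, so the absolute incidence is still inflated.

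**The case against.** The strongest reply is that little hangs on this.

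- **Safety is descriptive.** Protocol 9.4.2 plans no between-arm test, and the primary endpoint, sample size and efficacy analyses are untouched. This stands and limits the severity. It does not remove the point, because the incidence tables are the planned tolerability evidence.
- **Few such events may be recorded.** AEs are elicited by open, non-leading questions (Protocol 8.3.2), not derived from the diary, and expected symptoms of the studied disease are excluded. This also stands. A reader might equate every participant who misses the 2-point responder threshold with an AE and so infer a 20-point shift from 50% versus 70% non-response. The documents make no such link. A 20-point shift would also need no background TEAEs at all; at a 40% background the same rates give 12 points.
- **The events would be visible.** SAP 11.1 and 11.1.1 tabulate TEAEs by system organ class and preferred term and list all AEs. This stands in part and depends on coding. A preferred-term row shows how many participants had that term, not how many had only that term, so the effect on the any-TEAE total cannot be read from the table.

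A reader might also infer that SAE counts are as exposed as AE counts. The seriousness requirement in Appendix 3 argues against that.

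**Conclusion.** The contradiction is explicit, in current text, and unresolved in either document. TEAE incidence depends on which bullet a site follows, and the table of TEAEs leading to study discontinuation may depend on it too.

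The size is unknown. Under the assumed rates, the between-arm shift is about 3 to 9 points if all sites follow the second bullet, about half that if half of participants are at such sites, 12 points in the extreme case, and 0 if lack of efficacy is equally frequent in both arms. The shift favours safinamide only if lack of efficacy is recorded more often on placebo. That is plausible if the drug works, but whether it works is the trial's own question, so a bias towards safinamide is not established.

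Nor do the documents show which bullet was intended. A reader might take the second for a leftover to be struck out, but nothing in the text supports choosing it over the first. The point should be put right, but it does not threaten the primary result.

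**What to change.** 1. Reconcile the two Appendix 3 bullets into one rule on lack of efficacy, applied at all sites. Which rule to keep is for the sponsor to decide and state.
2. Make the change by the route the protocol requires. Protocol 10.1.1 calls for IRB/IEC approval of amendments before changes are implemented, so the sponsor should settle whether this is an amendment or a clarification.
3. State in the SAP how events reported only as lack of efficacy will be identified, and show TEAE incidence by arm with and without them. Rewording the protocol cannot undo reports already made under the conflicting text, so this is needed whichever rule is kept.
4. State in the SAP how a withdrawal for lack of efficacy is classified among the discontinuation reasons, so that the SAP 11.1.6 table follows the same rule.

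The cost is a small protocol change with whatever review it needs, a short SAP rule, and one extra table line. Sample size and the efficacy analyses do not change.
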